Drug utilisation study (DUS) on flupirtine-containing medicinal products.

Retrospective drug utilisation study using patient-level databases to characterise prescribing practices of flupirtine-containing medicinal products during routine clinical use and assess the main reasons for prescription by representative groups of prescribers.

Rationale and background

Due to a rising number of hepatotoxicity reactions during treatment with flupirtine containing products the Co-ordination Group for Mutual Recognition and Decentralised Procedures – Human (CMDh) recommended on 28 June 2013 to restrict the use of oral Flupirtine medicines and suppositories as following:

- treatment of acute (short-term) pain in adults who cannot use other painkillers, such as non-steroidal anti-inflammatory drug (NSAIDs) and weak opioids
- treatment duration limited to not longer than 2 weeks
- after each full week of treatment patients' liver function should be checked
- treatment termination if any signs of liver problems occur
- contraindicated for patients with preexisting liver disease or alcohol abuse problems
- contraindicated for patients taking other medications known to cause liver problems

The recommendations follow a review by the EMA's Pharmacovigilance Risk Assessment Committee (PRAC) which looked into reported liver problems with Flupirtine, ranging from high liver-enzyme levels to liver failure. The PRAC evaluated the available data on liver safety, noting that there were no cases of liver failure or liver transplantation reported in patients who took the medicine for 2 weeks or less. The PRAC also reviewed the available data on the benefits of Flupirtine and concluded that, while there were data from studies in the treatment of acute pain, there were insufficient data to support its use in the treatment of long-term pain.

The CMDh agreed with the PRAC's conclusions and endorsed the PRAC's recommendations on the use of flupirtine-containing medicines. The CMDh position was sent to the European Commission (EC), which endorsed it and adopted a final legally binding decision valid throughout the EU on 5 September 2013.

The reported outcomes were communicated to healthcare professionals by all Germany marketing authorisation holders (MAHs) via a joint Direct Healthcare Professional Communication (DHPC) distributed in July 2013.

The Summaries of Product Characteristics (SmPCs) for flupirtine-containing medicinal products have been revised accordingly by Lupin in February 2014 and MAHs marketing flupirtine-containing medicinal products in Germany in September/October 2013.

Additionally the PRAC requested that the MAHs should submit a risk management plan (RMP). The protocols of two studies - a drug utilisation study (DUS) and a PASS - should be submitted as part of the RMP.

This protocol covers a design for a DUS based on the information captured in longitudinal patient-level databases and has been set up accordingly to fulfill the conditions of the authority.

Research question and objectives

The aims of this study are to characterise prescribing practices for flupirtine-medicinal products during routine clinical use and to evaluate co-prescriptions and therapies of patients treated with Flupirtine products before and after the revision of the SmPC.

The analysis will display:

- Number of Flupirtine patients per specialty, per region (East/West Germany) and overall patients in the office
- Patient demography (age, gender and insurance status)
- Diagnoses, related to Flupirtine prescriptions
 - Diagnoses explicitly associated with Flupirtine prescriptions
 - Co-diagnoses associated with Flupirtine prescriptions
- Therapies, related to Flupirtine patients
 - Co-prescriptions received by Flupirtine patients
 - Further therapies received by Flupirtine patients
- Flupirtine exposure
 - Dosage and therapy duration
 - Prescription length
 - Number of Flupirtine prescriptions
 - Single and repeat prescriptions
 - relevant treatment patterns if available
- Contraindications for use of NSAIDs or weak opioids
- Long-term medications (>14 days) leading to contraindications for the use of Flupirtine
- Liverfunctions test, if available within 1 week after exposure to Flupirtine

Study design

This study is implemented using a longitudinal patient level Electronic Medical Records (EMR) database for Germany, IMS[®] Disease Analyzer.

The DUS will be carried out in Germany as more than 90% of total prescriptions for flupirtine-containing medicinal products of MAHs in European Union Member States were issued in Germany.

Population

The study will capture patients in the outpatient setting in Germany. All patients who have received at least one prescription for a flupirtine-containing product within a defined 12-month period (patient selection window) in the selected data sources will be included in the analysis. The analysis will consist of 2 time periods, the first one the year 2012 as time frame before and the second one the year 2014 as time frame after the SmPC revision.

Variables

The following variables will be extracted from the database:

- Prescription of a flupirtine-containing medicinal product
- Specialty and type of prescribing physician

- Demographical characteristics of patients treated with flupirtin (age, gender, insurance)
- Indication for Flupirtine treatment (reasons for prescription)
- Duration of Flupirtine treatment recommended by the physician
- Daily Flupirtine dose recommended by the physician
- Prescription length
- Concomitant prescriptions of drugs
- Co-diagnosis
- Liverfunction tests

Data sources

The following data sources will be used: IMS[®] Disease Analyzer (DA); primary care physician (PCP) and orthopaedist panels. Both panels cover more than 95% of all Flupirtine prescriptions in Germany.

Study size

All patients in the PCP and orthopaedist panel recorded during the analysis periods 2012 and 2014 of the IMS[®] DA will be considered for the study. The study size per period will include approximately 1,300 patients treated with Flupirtine in the orthopaedist panel of the IMS[®] DA database and approximately 8,400 patients treated in the PCP panel.

Data analysis

The statistical analysis will be done descriptively and performed separately for each physician panel. All analyses will be stratified by incident and prevalent users. Missing values will be reported as missing and no imputation will be conducted. Descriptive tables will be made for all variables.

Milestones(planned)

Start of data collection (reference period):	January 1, 2012
End of data collection (reference period):	December 31, 2012
Start of data collection (assessment period):	January 1, 2014
End of data collection (assessment period):	December 31, 2014
Registration in the EU PAS register:	Registration is planned prior to study initiation once the protocol is final and approved by BfArM
Final study report:	February 29, 2016

During the analysis time the following points and related time periods required have to be taken into account:

- Data will be available 6-8 weeks after end of data collection
- Data cleaning will last 2 weeks

- Statistical analysis, quality control and internal review will be performed within 6-8 weeks
- The study report will be created within 4 weeks

The start and end of data collection refers to the selection window for Flupirtine prescriptions. In addition a 12-month period before Flupirtine exposure start will be tracked. Additionally patients with at least 1 to 6 months follow up period after first exposure start date for each of both periods will be selected to obtain maximum information. For patients with longer observational period, the analysis will be performed until end of collection time if available.

5. Amendments and updates

None

6. Milestones

The study will start after the BfArM approval of the final study protocol.

Milestone: before and after SmPC review	Planned date
Start of data collection - Reference period	January , 1 2012
End of data collection - Reference period	December 31, 2012
Start of data collection – Assessment period	January 1, 2014
End of data collection - Assessment period	December 31, 2014
Registration in the EU PAS register	Registration is planned prior to study initiation once the protocol is final and approved by BfArM
Final report of study results	February 29, 2016

During the analysis time the following points and related time periods required have to be taken into account:

- Data will be available 6-8 weeks after end of data collection
- Data cleaning will last 2 weeks
- Statistical analysis, quality control and internal review will be performed within 6-8 weeks
- The study report will be created within 4 weeks

The start and end of data collection refers to the selection window for Flupirtine prescriptions. In addition a 12-month period before Flupirtine exposure start will be tracked. Additionally patients with at least 1 to 6 months follow up period after first exposure start date for each of both periods will be selected to obtain maximum information. For patients with longer observational period, the analysis will be performed until end of collection time if available.

7. Rationale and background

Flupirtine, a non opiotic analgetic drug for acute and chronic pain relief was first introduced in the European Union in 1984 as an alternative analgesic to opioids and NSAIDs. During the use of this selective neuronal potassium channel opener (SNEPCO) other pharmacological impacts such as a reduction in muscle tension have been observed.

The German Federal Institute for Drugs and Medical Devices (BfArM) induced an urgent union procedure under Article 107i of Directive 2001/83/EC on February, 28th 2013 and signaled its intention to restrict the use of all flupirtine-containing

medications to short term treatment of acute pain and to withdraw the indication of use in chronic pain¹.

This intention from BfArM was based on a rising number of observed liver effects spontaneously reported during Flupirtine treatment while evaluating pharmacovigilance data. The effects range from asymptomatic liver enzyme elevation to fatal liver failure or liver transplantation were received. BfArM reported a total number of 954 records in their German adverse drug reaction database for Flupirtine including 330 reports for the system organ class (SOC) hepatic and biliary disorders (according to Common Terminology Criteria for AEs, CTCAE). Liver failure was reported in 49 cases including 12 cases with fatal outcome and 3 cases with liver transplantation. Flupirtine treatment lasted 60 days in average. In 25 of the above 49 cases (51%) a co medication with potential hepatotoxic effect was administered.

The growing number of Flupirtine prescriptions in Germany and thus the steadily increasing patient exposure was embraced to be associated with the rising number of reported Adverse Drug Reactions (ADRs). Additionally, a lack of the minimum requirement in the efficacy data of Flupirtine of at least three months treatment in controlled clinical studies for mild to moderately severe chronic nociceptive pain was denounced by the BfArM².

Considering the above safety concerns and further consideration of the current evidence for the efficacy of Flupirtine in the treatment of acute and chronic pain, the BfArM came to the conclusion, that the benefit-risk balance was potentially favourable in acute pain, implementing strict treatment restrictions (e.g. treatment duration limited to 2 weeks, frequent liver tests) and unfavourable in the treatment of chronic pain.

The PRAC initiated a subsequent benefit-risk evaluation and considered that the controlled clinical studies required by the Note for guidance on clinical investigation of medicinal products for treatment of nociceptive pain (CPMP/EWP/612/00, issued 21 November 2002) for long-term treatment of chronic pain are not available for flupirtine-containing medicinal products². Based on the fact of observed liver effects recorded during long-treatment with Flupirtine and on the absence of controlled long-term clinical studies, the PRAC noted that the management of chronic pain is no longer favourable in terms of the benefit-risk balance for flupirtine-containing medicinal products. The PRAC adopted a recommendation on 13 June 2013 under the provisions of article 107i of Directive 2001/83/EC³.

Taking the currently available data into account, the PRAC decided that the benefit-risk balance for flupirtine-containing products is favourable in the treatment of acute pain, subject to implementation of the following risk minimisation measures⁴:

- Limitation of indication to acute pain in adults if treatment with other analgesics (e.g. NSAIDs, weak opioids) is contraindicated.
- Restriction of Flupirtine use to a maximum of two weeks of treatment.
- Contraindication of Flupirtine in patients with pre-existing liver disease or alcohol abuse.
- Contraindication of Flupirtine in patients concomitantly taking other medications which are known to cause Drug Induced Liver Injury (DILI).

- Weekly liver function tests during treatment and discontinuation in the case of abnormal liver function tests or clinical symptoms.

The PRAC imposed a DHPC, which was distributed on 15 July 2013, in order to communicate the outcome of the PRAC/EMA decision to healthcare professionals⁵. The SmPCs for flupirtine-containing medicinal products have been revised accordingly by Lupin in February 2014 and MAHS marketing flupirtine-containing medicinal products in September/October 2013⁶. The educational material was distributed in February 2015.

Patients and prescribers have been provided with joint educational material according to the PRAC request, prepared jointly by all German MAHs. The educational material, the DUS and a PASS protocol are parts of the RMP.

As of 5 September 2013, the European Commission implemented the decision (C(2013) 5788 final) with the majority opinion of the CMD(h) addressed to all member states based on the PRAC's recommendation⁷.

Additionally the PRAC requested that the MAHs should submit a risk management plan (RMP) within 3 months after the EC decision. The protocols of two studies - a drug utilization study (DUS) and a PASS should be submitted as part of the RMP.

Hormosan Pharma GmbH launched Flupirtinmaleat-Hormosan 100 mg Hartkapseln in Germany on 31 July 2012, but the marketing of the product was stopped in January 2013. This decision was taken because of commercial and not for safety reasons. Any other MAs held by Lupin Group of companies within EU have not been launched yet. Therefore an extension of deadline for submitting the RMP (including the outline of DUS, PASS and educational material) was received by the Reference Member State (RMS) authority BfArM on 29 November 2013 as the products are currently not marketed.

This protocol covers a design for a DUS based on the information captured in longitudinal patient-level databases and has been designed to fulfill the conditions of the authority.

8. Research question and objectives

The Flupirtine DUS aims to characterise prescribing practices of flupirtine-medicinal products during routine clinical use and to assess the main reasons for prescription by representative groups of prescribers.

The analysis will display by specialty and by prevalent/incident status:

- Number of prescribing physicians
- Region of office (East/West Germany)
- Number of overall patients in the office
- Number of patients with at least one flupirtine containing product

- Patient characteristics: age, gender, insurance status, indication for Flupirtine prescription
- Flupirtine exposure:
 - Number of Flupirtine prescriptions per patient during the 12-month observation period
 - Recommended daily Flupirtine dose (by physicians)
 - Recommended Flupirtine treatment duration (by physicians)
 - Prescription length
 - Indications related to the Flupirtine prescription
 - Co diagnosis within analysis period
 - Concomitant prescription of drugs grouped by relevant ATC classes (Annex 3- ii)
- Administered long-term medications (>14 days) leading to contraindication use of Flupirtine
- Contraindications for use of NSAIDs or weak opioids
- Treatment patterns if available
- Liverfunctions test performed within 1 week after Flupirtine exposure start

9. Research methods

9.1. Study design

This drug utilisation study for Flupirtine will employ an analysis using a longitudinal database in Germany:

- Patient level electronic medical record (EMR) data (IMS[®] Disease Analyzer)

The IMS[®] Disease Analyzer provides both drug use data and information about patients' clinical characteristics, including indication, co-morbidities and laboratory tests in separate physician panels.

The study will be carried out in Germany as more than 90% of total prescriptions of flupirtine-containing medicinal products of MAHs in European Union Member States were issued in Germany.

The study will be set up as a pre-post design to compare flupirtine prescribing patterns (before and after the revision of SmPC).

9.2. Setting

The study will be conducted in the outpatient setting in Germany.

Study population

All patients with a record of Flupirtine prescription during the defined 12-month periods (patient selection window) will be identified from selected database.

The study will include both single users and recurrent users of flupirtine-containing medicinal products.

The study will include two cohorts of patients:

- patients initiated on flupirtine treatment after the review of SmPC in Germany
- patients treated with flupirtine before the review of SmPC in Germany

The two cohorts will include:

- Incident user: patients who had one or more flupirtine prescriptions during the one-year observational period, but no flupirtine prescription for at least 12 months prior to the first flupirtine prescription during the observational period
- Prevalent user: patients who had one or more flupirtine prescriptions during the one-year observational period and at least one flupirtine prescription during the 12 months prior to the first flupirtine prescription during the observational period

Inclusion criteria:

Eligible patients must have at least one prescription of Flupirtine (exposure) during the defined 12-month observational period.

Exclusion criteria:

Exclusion criteria will not be applied.

Study period

The selection of patients from the IMS[®] Disease Analyzer will be carried out in two defined 12-month periods from January 1, 2012 to December 31, 2012 and January 1, 2014 to December 31, 2014, respectively (patient selection window). The date of the first prescription fill in each period will be defined as the exposure start date.

Pre-exposure period:

In order to obtain information about medical history before Flupirtine exposure start, a time period of at least 12 months prior to the individual Flupirtine exposure start date will be analysed for each patient for whom these data are available.

Follow-up:

A follow-up period of one to six months after the exposure start date will be monitored for all patients, and till the end of analysis period for whom these data are available.

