9.4. Data Sources

The IMS[®] Disease Analyzer, a German longitudinal patient-level database will be used as data source for the Flupirtine utilization study.

IMS[®] Disease Analyzer

IMS[®] Disease Analyzer is a database which continuously receives anonymised data reported from approximately 3,000 office-based physicians* (including specialists such as cardiologists, gynaecologists, neurologists, orthopaedists, or urologists) representing approximately 2.4% of all practices* in Germany. The database contains longitudinal data from more than 11 million observational profiles documented over the last 3 years.

The data are generated directly from the electronic medical records of the panel physicians' practice via standardized interfaces and provide daily routine information on patients' diseases and therapies. The main parameters routinely collected in the IMS[®] Disease Analyzer database are presented in Table 1. The lag time of data availability is 6 weeks.

The IMS[®] Disease Analyzer PCP panel consists of 1,141 PCPs (general practitioners [GPs] and internists without subspecialty) and 177 orthopaedists selected using a pre-specified random plan as described by Becher et al. (2009) in their paper verifying the validity and representativeness of the IMS[®] Disease Analyzer patient database in Germany⁸.

* No personal data but exclusively anonymous information (in accordance with § 3 Abs. 6 "Bundesdatenschutzgesetz" – German Federal Data Protection Act).

Table 1: Variables included in the IMS[®] Disease Analyzer database

Category	Nature of data	Variables
Patient data	Characteristics	Age, sex, insurance(private or SHI insured)
	Diagnoses	Date of diagnosis, ICD-10, original text, co-morbidity, laboratory tests and results
	Therapy	Date of visit, product and quantity, molecule, ATC, dosage scheme, co-prescription

The German IMS[®] Disease Analyzer database has been previously used to answer a wide range of research questions^{9,10,11,12}. In addition, the IMS[®] Disease Analyzer database is used by the European Medicines Agency (EMA) as one of its resources for answering research questions.

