9.5. Study size

All patients in the PCP and orthopaedist panel of the IMS[®]DA fulfilling the selection criteria will be considered for the study.

A preliminary count of patients treated with Flupirtine over a 12-month period (July 2013 to June 2014) gave the sample sizes for the selected IMS[®] DA panels (presented in Table 2). As acute pain treatment has no seasonal impacts, the 12 months period and not a calendar year period is acceptable for feasibility appraisal.

Table 2: Number of patients with flupirtine-containing prescriptions in the IMS[®] Disease Analyzer from July 2013 to June 2014

IMS [®] DA Panel	Number of Flupirtine patients	Number of Flupirtine patients with at least 12 months history	Number of Flupirtine patients with at least 12 months history (25% reduction)
PCP	14,743	11,284	8,463
Orthopaedist	4,635	1,821	1,365

Taking into account the sample sizes and a further 25% reduction for a hypothetical decrease in Flupirtine prescriptions over the planned observation period compared to the period evaluated in 2014, we expect that the minimum number of Flupirtine patients available for the analysis will be not lower than about 8,400 and 1,300 patients in the DA PCP and orthopaedist panel, respectively. The more data are available, the higher the level of confidence on any estimates, i.e. the smaller the width of the 95% confidence interval.

Similar Flupirtine patient counts for the DA database are expected for the 12-month selection window of the Flupirtine DUS.

The study size of the Flupirtine DUS is expected to range from approximately 1,300 Flupirtine patients in the orthopaedist panel of the IMS[®] DA database. The study size is based on the number of patients with Flupirtine prescriptions in the 12-month period from July 2013 to June 2014, so the study size of the planned 12-month patient selection window in the Flupirtine DUS may be slightly different.

The 12-month patient selection window is considered to be sufficient to provide representative for prescribing practices during the routine clinical use of flupirtine-containing medicinal products in Germany.

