9.7.2.4 Comparison of the patient/prescriptions of the two observational periods

The comparison of the patients/prescriptions of the two observational periods (assessment period and reference period) based on IMS[®] Disease Analyzer data will consider the following parameters. The comparisons will be performed separately by physician panel and will be stratified by incident and prevalent users:

- Number and percentage of patients with any diagnosis of disease contraindicated for NSAIDs or weak opioids
- Number and percentage of prescriptions with diagnosis associated with acute pain
- Number and percentage of patients with single and repeated flupirtine prescriptions within the defined time period
- Number and percentage of prescriptions with LFT monitoring during flupirtine treatment
- Length of treatment episodes
- Number and percentage of patients with at least one treatment episode longer than 14 days (based on DDD)

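### The planned 2012 versus 2014 tables cannot show whether a difference reflects changed prescribing or a changed set of reporting practices

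*Protocol*

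**What the plan says.** Section 9.1 of the protocol describes the design: "The study will be set up as a pre-post design to compare flupirtine prescribing patterns" before and after the SmPC revision. The two selection windows are calendar years 2012 and 2014. Section 9.2 sets the population: "All patients with a record of Flupirtine prescription during the defined 12-month periods (patient selection window) will be identified from selected database". It adds: "Exclusion criteria will not be applied". No condition is placed on the practice.

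Section 9.7.2.4 lists what is compared between the years: recorded contraindications to NSAIDs or weak opioids, acute-pain diagnoses, single and repeated prescriptions, liver function testing, episode length, and episodes over 14 days. It fixes the strata: "The comparisons will be performed separately by physician panel and will be stratified by incident and prevalent users". Section 9.7.1 makes the analysis descriptive and links the period comparison to the effect of risk minimisation measures.

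Section 9.4 gives the panel size once, without a date: the "PCP panel consists of 1,141 PCPs (general practitioners [GPs] and internists without subspecialty) and 177 orthopaedists selected using a pre-specified random plan". It says nothing about practices joining or leaving. Section 9.8 states that panel representativeness is checked continuously. Section 9.9 lists limits such as specialty balance, care outside the practice and no tracking across panels, but not changing panel membership.

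**The concern.** The compared outcomes are largely habits of prescribers: how often they repeat a prescription, order liver tests or code a contraindication. If the practices reporting in 2014 are not those reporting in 2012, the contrast partly compares different prescribers. A shift in membership could then create or hide a change that would be read as an effect of the restrictions. The orthopaedist panel, with 177 physicians, is the more exposed.

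Membership can also affect the strata. Incident use means no flupirtine prescription in the preceding 12 months, but section 9.2 examines that look-back only where data are available. In a practice that has just joined, a continuing user could be classed as incident. This is why the look-back years matter as well as the two windows.

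**Working it through.** **Inputs from the protocol.** Table 2 in section 9.5, for July 2013 to June 2014, gives 11,284 PCP and 1,821 orthopaedist patients with at least 12 months of history, and a 25% reduction. Section 9.4 gives 1,141 PCPs and 177 orthopaedists.

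**The plan's own figures.** 11,284 × 0.75 = 8,463, and 1,821 × 0.75 = 1,365.75 (stated as 1,365). Both reproduce. Per physician this is 8,463 / 1,141 = 7.4 and 1,365 / 177 = 7.7 expected patients.

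**Sampling error for a period difference.** The unclustered 95% half-width at p = 0.5 with n patients per period is 1.96 × √(2 × 0.25 / n).
- PCP: 1.96 × √(0.5 / 8,463) = 1.5 points.
- Orthopaedist: 1.96 × √(0.5 / 1,365) = 3.8 points.

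**Possible artefact if replacement is systematic.** Prescribing is held unchanged in every practice. The artefact is the share of patients in replaced practices times the difference in outcome between leaving and joining practices. The protocol gives neither, so both are assumptions.
- 10% replaced, 15-point difference: 0.10 × 15 = 1.5 points.
- 30% replaced, 15-point difference: 0.30 × 15 = 4.5 points.
- Widening the assumed difference to 10 to 30 points gives 0.10 × 10 = 1 point up to 0.30 × 30 = 9 points.

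**Possible artefact if replacement is like for like.** The expected difference is zero and only noise remains. Assume equal practice sizes and a between-practice standard deviation of 20 points. The 95% range is ±1.96 × turnover × 20 × √(2 / replaced practices).

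| Panel | Turnover | Replaced practices | 95% range (points) |
|---|---|---|---|
| PCP | 10% | 114.1 | ±0.5 |
| PCP | 30% | 342.3 | ±0.9 |
| Orthopaedist | 10% | 17.7 | ±1.3 |
| Orthopaedist | 30% | 53.1 | ±2.3 |

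All four lie below the sampling half-widths of 1.5 and 3.8. Systematic replacement under the 15-point assumption can reach or exceed them.

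**Precision cost of a stable-practice set.** If the restriction loses 10% to 30% of patients (assumed), the PCP panel keeps about 7,617 to 5,924 per period and the half-width becomes 1.6 to 1.8 points. The orthopaedist panel keeps about 1,228 to 955 and the half-width becomes 4.0 to 4.5 points.

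**The case against.** The strongest reply is that two representative yearly samples validly describe national change, and section 8 aims at representative groups of prescribers. Physicians are chosen by a pre-specified random plan and representativeness is monitored. If replacement is like for like, the artefact is small noise, and nothing in the document suggests otherwise. This stands as a limit on size. It does not close the gap: two representative panels can hold different practices, and the planned tables would not show the overlap.

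Practices reporting without a break for four years are a selected subset. That also stands, and is why their result should not automatically override the main one.

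Some safeguards exist. Sections 8 and 9.3 tabulate prescribing physicians, region and office patients, so a change in the number of prescribers would be visible, though not a change in who they are. Section 6 speaks of selecting patients with at least one to six months of follow-up, which limits truncation when a practice leaves mid-year, although its wording is loose.

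A sensitivity analysis could sit in a statistical analysis plan that is not shown. The population rule, the comparison strata and the list of limitations, however, are fixed in the protocol itself.

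A reader might infer turnover from the protocol's own counts. Section 9.4 reports about 15,000 orthopaedist and 39,000 PCP patients over 24 months (August 2011 to July 2013), so an average year has at least 7,500 and 19,500. Against 4,635 and 14,743 in Table 2, the falls are 38% and 24%. But the Table 2 window opens in the month of the healthcare professional letter (15 July 2013) and spans the SmPC revisions, which could explain them. Nor does the share of patients under Table 2's column "Number of Flupirtine patients with at least 12 months history" prove turnover: 1,821 / 4,635 = 39% for orthopaedists against 11,284 / 14,743 = 77% for PCPs could reflect episodic specialist care. Neither figure should be cited as evidence that practices changed.

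**Conclusion.** The point holds as a gap in the planned comparison. The protocol fixes a before-and-after contrast, linked to the effect of risk minimisation measures, on whichever practices report in each year, and no planned table shows how far the two sets of practices overlap. The documents do not show that membership changed, and the size of any bias is unknown. The 1.5 to 4.5 points rest entirely on assumed turnover of 10% to 30% and an assumed 15-point difference; under like-for-like replacement the average bias is near zero.

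A reader might conclude that changed prescribing and changed membership cannot be separated at all. That goes too far. Counting prescribing physicians and patients per office implies that practices can be identified, so the limit lies in the planned analysis and probably not in the data.

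**What to change.** Keep the all-practice comparison as planned, and make three additions.

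- **Section 9.7.2.4:** a sensitivity analysis repeating each listed comparison in practices that contributed data continuously from January 2011 to December 2014, which covers both windows and their look-back years.
- **Reporting:** the number of contributing practices per panel and period, and the number common to both periods.
- **Section 9.9:** name changing panel membership as a limitation, and state that where the two results differ, the change cannot be attributed to the risk minimisation measures alone.

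The work is one practice-level filter and a second run of the comparison tables. The cost is wider intervals, mainly for orthopaedists, and a set of practices that may be less representative. The stable-practice result should therefore be read beside the main result and not automatically replace it.
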